4.4.1.5.10 HIV viral load

The following HIV viral load indicators will be derived after each injection:

- Increase in HIV viral load: Yes, if plasma HIV-1 RNA < 50 copies/mL pre-injection and > 1000 copies/mL post-injection, not explained by non-adherence to ART and not explained by any other possible etiology, otherwise No, if pre- and post-injection HIV viral load are valid and not missing; Missing if either pre- or post-injection HIV viral load is missing or non-valid.
- Confirmed increase in HIV viral load: Yes, if plasma HIV-1 RNA < 50 copies/mL pre-injection and > 1000 copies/mL post-injection, not explained by non-adherence to ART and not explained by any other possible etiology and a second test taken 4 weeks after the first (ie,

approximately 2 months post-injection) also shows plasma HIV-1 RNA > 1000 copies/mL, otherwise No, if pre- and post-injection HIV viral load are valid and not missing; Missing if there is missing or non-valid pre- or post-injection HIV viral load value in the first or second test.

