6.7 Concomitant Medications and Other Therapies

At the time of enrollment, ongoing medications and other therapies (eg, blood products) should be recorded in the source document as well as new medications prescribed for new medical conditions / AEs during study participation.

Documentation in the CRB of ongoing concomitant medication(s) will be limited to specific categories of medication(s) of interest beginning on the day of vaccination. This may include medications of interest that were started prior to the day of vaccination.

Reportable medications will be collected in the CRB from the day of each vaccination to the end of the solicited and unsolicited follow-up period (eg, 28-day safety follow-up) as they may impact the response to the vaccination and impact the consistency of the information collected on concomitant medications at any vaccination.

Reportable medications include medications that impact or may impact the consistency of the safety information collected after any vaccination and/or the immune response to vaccination. Three standard categories of reportable medications are defined:

- Category 1: medications impacting or that may have an impact on the evaluation of the safety (eg, antipyretics, analgesics, and non-steroidal anti-inflammatory drugs [NSAIDs], steroids/corticosteroids). *Note: inhaled and topical steroids should not be captured.*
- Category 2: medications impacting or that may have an impact on the immune response.
 - Immunosuppressive therapy such as anti-cancer chemotherapy or radiation therapy or long-term systemic corticosteroids (for more than 2 consecutive weeks) in the 4 weeks after study injection
 - Immune globulins, blood or blood-derived products in the 3 months before the first study injection, in the 4 weeks before second and third injection, and in the 4 weeks after any injection
 - Any vaccine (other than the study vaccine) in the 4 weeks before second and third injection, and in the 4 weeks after any injection
- Category 3: medications impacting or that may have an impact on both the safety and the immune response (eg, steroids/corticosteroids)

The information reported in the CRB for each reported medication will be limited to:

- Trade name.
- Origin of prescription: prophylaxis Yes/No. Medication(s) prescribed for AE prophylaxis will be recorded in the Action Taken of the AE collection tables.
- Medication category (1, 2, or 3).
- Start and stop dates.

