2.2 Secondary Objectives

Immunogenicity:

- To describe the humoral immune response to each dengue serotype at baseline and 28 days after each injection of CYD dengue vaccine in HIV-positive adults previously exposed to dengue.

Safety

- To detect the CYD dengue vaccinal viremia post-Injection (post-Inj) 1 in HIV-positive adults previously exposed to dengue.
- To describe changes in CD4 count and HIV ribonucleic acid (RNA) viral load after each injection of CYD dengue vaccine in HIV-positive adults previously exposed to dengue.

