4.4.1.5.9 CD4 Count

The standardization of CD4 count will be performed using the International System Units if different units appear (eg, if more than one laboratory is involved).

Change in CD4 count after each injection will be calculated in percentages (%) for the derivation of decrease in CD4 count as

$$\frac{CD4\ count\ prior\ to\ vaccination - CD4\ count\ post\ vaccination}{CD4\ count\ prior\ to\ vaccination} \times 100\%$$

The following CD4 count indicators will be derived after each injection:

- Decrease in CD4 count $> 30\%$ post-injection compared to the pre-injection values (ie, percentage change in CD4 count $> 30\%$), not explained by non-adherence to ART and not explained by any other possible etiology: Yes, if the decrease in CD4 count $> 30\%$, otherwise No, when pre- and post-injection CD4 counts are valid and not missing; Missing if either pre- or post-injection count is missing or non-valid.
- Confirmed decrease in CD4 count $> 30\%$ post-injection compared to the pre-injection values (ie, percentage change in CD4 counts $> 30\%$), not explained by non-adherence to ART and not explained by any other possible etiology: Yes if the second test taken 4 weeks after the first (ie, approximately 2 months post-injection) also shows a decrease in CD4 $> 30\%$, otherwise No, if pre- and the two post-injection CD4 counts are valid and not missing; Missing if there are missing or non-valid pre- or post-injection CD4 counts in the first or second test.

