5.1.2.2 Statistical Methods

For descriptive purposes, the statistics presented on Table 5.1 will be produced.

The proportion of subjects with a detected and quantified CYD dengue vaccinal viremia (ie, above the detection level) whatever the serotype (as assessed by YF RT-PCR) and for each of the four dengue serotypes (by serotype-specific CYD RT-PCR method) after the first CYD dengue vaccine injection will be presented at V02 and V03.

Number of subjects and percentages having a decrease in CD4 > 30% post-injection compared to pre-injection values and confirmed decrease in CD4 > 30% after each injection, not explained by non-adherence to ART and not explained by any other possible etiology, as well as an increase in HIV viral load post-injection and confirmed increase in HIV viral load (ie, plasma HIV-1 RNA < 50 copies/mL pre-injection and > 1000 copies/mL post-injection) for each injection, not explained by non-adherence to ART and not explained by any other possible etiology will be presented.

Analysis of dengue neutralizing antibody levels will be performed in each vaccine group before first injection (at baseline) and 28 days after each injection using:

- GMTs against each serotype with the parental dengue virus strains
- GM of individual titer ratio (GMTR) against each serotype with the parental dengue virus strains (post-Injection 1/pre-Injection 1, post-Injection 2/pre-Injection 1, and post-Injection 3/pre-Injection 1)
- Number and percentage of subjects ≥ 10 (1/dil) against each dengue serotype with the parental dengue virus strains at each available time point
- Number and percentage of subjects ≥ 10 (1/dil) against at least 1, 2, 3, or 4 dengue serotypes with the parental dengue virus strains at each available time point
- Number and percentage of subjects \geq various titer thresholds (1/dil) against each dengue serotype with parental dengue virus strains at each available time point
- Number and percentage of subjects \geq various titer thresholds (1/dil) for at least 1, 2, 3, or 4 serotypes with parental dengue virus strains at each available time point
- Distribution of titers against each of the 4 serotypes with parental dengue virus strains at each available time point and corresponding RCDCs
- Number and percentage of subjects immune and non-immune to YF, dengue, Zika and FV statuses at baseline

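### The SAP tabulates a measured HIV RNA rise as no increase once it is attributed to another cause, words the CD4 rule two ways, and omits the protocol's unfiltered summary over time

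*SAP*

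**What the plan says.** **Objective and endpoint.** SAP 2.2 gives the aim as "To describe changes in CD4 count and HIV ribonucleic acid (RNA) viral load after each injection of CYD dengue vaccine", and Protocol 2.2 agrees. The endpoint in Protocol 9.2.1.2 is the two measurements 28 days after each injection. Neither carries a condition on cause.

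**HIV RNA (SAP 4.4.1.5.10).** The indicator is "Yes, if plasma HIV-1 RNA < 50 copies/mL pre-injection and > 1000 copies/mL post-injection, not explained by non-adherence to ART", with any other etiology excluded in the same sentence. The default is "otherwise No, if pre- and post-injection HIV viral load are valid and not missing". The confirmed indicator repeats the condition and adds a second test.

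**CD4 (SAP 4.4.1.5.9).** The label and the start of the rule read "not explained by non-adherence to ART and not explained by any other possible etiology: Yes, if the decrease in CD4 count" exceeds 30%, followed by "otherwise No, when pre- and post-injection CD4 counts are valid and not missing".

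**Analysis.** SAP 5.1.2.2 gives numbers and percentages of subjects with each indicator. It attaches the exclusion to the CD4 items and again to the viral-load items: "not explained by non-adherence to ART and not explained by any other possible etiology will be presented". SAP Table 5.1 has a categorical row for these indicators (number and percentage) and no continuous row for either marker. Protocol 12.1.2.2 promises a summary of both markers over time, with no filter. SAP 5.7, which lists changes to planned analyses, does not mention that summary.

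**Data behind the judgement.** Protocol 5.1.4 collects ART-related information at Screening and Visit 1, within medical history. It lists no adherence or regimen-change item from Visit 2 to Visit 8. Protocol 6.7 says "Documentation in the CRB of ongoing concomitant medication(s) will be limited to specific categories of medication(s) of interest beginning on the day of vaccination", and its three categories do not name ART. Protocol 6.6 on compliance concerns vaccine doses only.

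**The concern.** The exclusion also appears in the study-hold rule (Protocol 5.5) and the SAE reporting rule (Protocol 10.7), where the aim is to single out unexplained signals. The SAP uses the same clause to define a descriptive endpoint, where the aim is to report what happened to the laboratory values.

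In that role the clause can only lower a count, never raise it. It is applied after an abnormal value is known, and its second limb (any other etiology) is open-ended. Background causes such as missed doses and intercurrent infections are what a randomized placebo arm is there to show. Protocol 5.1.2 gives that as a reason for the design, and Protocol 1.3.2 raises the possibility of a transient rise in HIV viremia after vaccination.

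At stake is whether the CD4 and HIV RNA tables answer the stated objective. A row showing no viral-load increases would be compatible with measured rises above 1000 copies/mL in either arm.

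**Working it through.** **Step 1. Apply the rules to hypothetical subjects, all values valid.**

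| Subject | Laboratory change | Attribution | SAP result |
|---|---|---|---|
| A | HIV RNA <50 to 5000 copies/mL | unexplained | Yes |
| B | HIV RNA <50 to 5000 copies/mL | missed ART doses | No, kept in denominator |
| C | CD4 down 40% | unexplained | Yes |
| D | CD4 down 40% | intercurrent illness | Yes by the rule after the colon in 4.4.1.5.9; not counted by its label or by 5.1.2.2 |

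B is settled by the text: the result is neither Missing nor a separate category. D is not settled. Two programmers could each follow the SAP and disagree.

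**Step 2. Look for another SAP output that would show B's rise.** Table 5.1 and 5.1.2.2 offer only the filtered counts. The over-time summary in Protocol 12.1.2.2 would show it, but the SAP does not carry it over.

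**Step 3. Reproduce the plan's own figure.** Protocol 12.5 and SAP 5.5 state a 95% probability of observing an event with 3% true incidence in the vaccine group, n = 100.

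P(at least one) = 1 − 0.97^100 = 0.9524. The figure is reproduced.

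**Step 4. Scale of the effect.** Let f be the share of threshold crossings attributed to another cause. The documents give no value, so f is an assumption shown over a range. The tabulated incidence is 3% × (1 − f), and P = 1 − [1 − 0.03(1 − f)]^100.

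A table showing 0/100 has a Clopper-Pearson upper 95% limit of 1 − 0.025^(1/100) = 3.62%. That limit bounds only the unattributed incidence. The matching value for all crossings is 3.62% / (1 − f).

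| f | Tabulated incidence | P(at least one in 100) | All-cause incidence compatible with 0/100 |
|---|---|---|---|
| 0 | 3.00% | 95.2% | up to 3.6% |
| 25% | 2.25% | 89.7% | up to 4.8% |
| 50% | 1.50% | 77.9% | up to 7.2% |
| 75% | 0.75% | 52.9% | up to 14.5% |

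**Step 5. Effect on the comparison.** If blinding makes f the same in both arms, incidences p_v and p_p become p_v(1 − f) and p_p(1 − f). Their ratio is unchanged and their difference shrinks by the factor (1 − f).

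**The case against.** **Blinding.** Under Protocol 6.4 the observer investigator and the sponsor do not know the product given. This stands. A reader might infer that the clause favours the vaccine arm; the documents do not support that, because attribution by a blinded investigator should fall on both arms alike. What blinding does not cure is the lower count in each arm.

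**CD4.** A reader might infer that an explained CD4 fall is definitely coded No. The operative rule in SAP 4.4.1.5.9 is numeric, so the supportable point is inconsistent wording.

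**Other outputs.** A reader might infer that explained changes vanish altogether. The raw values stay in the database, the protocol still promises its summary, and every crossing triggers a second sample four weeks later. The supportable point is that the SAP omits the summary without listing the change. AE tables are only a partial backstop. Protocol 10.7 requires SAE reporting for unexplained changes only. The 28-day sample may also be drawn up to day 42 (28 + 14), while SAP 4.4.1.2.3 lists, and does not analyse, unsolicited AEs with onset after day 28.

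**Evidence for the judgement.** A reader might infer that there is none. That goes too far: intercurrent illness is captured as unsolicited AEs up to 28 days, and Protocol 6.7 requires ongoing and newly prescribed medications in source documents. The gap is narrower. No post-injection adherence item is listed, and neither document names who makes the judgement for the tables or in which CRF field it sits. The CRF itself is not available.

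**Rarity.** Inclusion criteria 5 and 6 require suppressed virus, CD4 above 350 cells/mm3 and stable ART for at least a year, so crossings above 1000 copies/mL may be few. This is plausible. It limits the likely size but does not justify coding those that occur as No.

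**Conclusion.** The point holds in this form. For HIV RNA, the SAP codes an attributed rise as no increase and keeps the subject in the denominator. For CD4, the SAP contradicts itself on whether the exclusion applies. These counts are the only CD4 and HIV RNA results the SAP plans. They do not describe changes as the objective requires, and the protocol's unfiltered summary has dropped out without being listed as a change.

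The main harm is under-counting in both arms, which rests on attribution being made blind. Its size cannot be derived, because neither document gives an attribution rate. The 3% incidence in the working is borrowed from the plan's sample-size statement and the values of f are assumed, so the results show scale and are not predictions. There is no error of power or sample size: the 95% figure is correct for events counted regardless of cause.

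**What to change.** 1. In SAP 4.4.1.5.9, 4.4.1.5.10 and 5.1.2.2, define the main indicators on laboratory values alone: CD4 fall above 30%, and HIV-1 RNA from below 50 to above 1000 copies/mL. Do this for the unconfirmed and confirmed versions, by arm and injection.
2. Show the version restricted to unexplained changes as a second row under each indicator.
3. Align the CD4 label, the CD4 rule and SAP 5.1.2.2 so that each row has a single definition.
4. Restore the summary of CD4 count and HIV-1 RNA over time from Protocol 12.1.2.2, and add matching continuous rows to SAP Table 5.1.
5. Leave the hold rule in Protocol 5.5 as it is.

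Optional: record missed ART doses or regimen changes at Visits 4, 6 and 8, if still feasible. This changes data collection and may need an amendment under Protocol 5.4. The SAP already describes part of the data review in the past tense (5.6), so it may come too late. The fix does not depend on it.

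Cost: SAP wording, a few extra table rows, and counts that may look less favourable. Items 1 to 4 need no new data.

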4.4.2 Immunogenicity

4.4.2.1 Computed Values for Analysis

For the computation of geometric mean titers (GMTs), a titer reported as < LLOQ will be converted to a value of 0.5 LLOQ.

For calculating titer ratio (geometric mean titer ratio [GMTR]), < LLOQ will be converted to 0.5 LLOQ for a numerator and < LLOQ will be converted to LLOQ for a denominator. If both numerator and denominator are < LLOQ, then both will be converted in the same way so that titer ratio=1.

There is no upper limit of quantification (ULOQ) with the plaque reduction neutralization test (PRNT) method planned.

4.4.2.2 Calculation Rules for the “at least X serotype(s)” Tables

The criteria below will be computed for each subject and visit as soon as at least one of the 4 dengue serotype results is different from missing or not-reportable (NR) (ie, coded no result in the serology database):

- Number and percentage of subjects with antibody titer ≥ 10 (1/dilution [dil]) against at least 1, 2, 3, or 4 serotypes with the parental dengue virus strains.
- Number and percentages of subjects with antibody titer \geq various titer thresholds (1/dil) against at least 1, 2, 3, or 4 serotypes with the parental dengue virus strains.

Titer(s) \geq to a threshold for at least X serotype(s) with parental dengue virus strains is computed as a Yes/No/Missing variable (note: in the case no titer is available the variable will be missing). If at least X among the 4 serotype titers meet the threshold considered then the variable is derived to “Yes”, otherwise if at least one titer is available and does not meet the threshold the variable is derived to “No”. For the percentage calculation, all the subjects with at least one titer available regardless of the serotype will be considered in the denominator.

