4.4.2.3 Baseline FV (dengue, YF, and Zika) Status

Baseline FV status is defined as the presence of neutralizing Abs against YF virus and/or Zika virus and/or positive Anti-NS1 ELISA result in the blood sample collected at V01 before vaccination in the present study from all subjects.

- **Immune:** subjects with quantified (\geq LLOQ) neutralizing Abs against YF virus, and/or Zika virus (≥ 100), and/or positive Anti-NS1 ELISA result.
- **Non-immune:** subjects without quantified (< LLOQ) neutralizing Abs against YF and without Ab against Zika (< 100) and negative Anti-NS1 ELISA result. To be classified in this

category, the titer results at baseline must be available and valid, ie, not coded ‘NR’ in the serology database.

- **Missing:** subjects with all the titer values missing.
- **Undetermined:** subjects do not meet the criteria for at least one of the above three categories, eg, a subject with a value < LLOQ against YF virus and/or Zika virus (<100) and/or negative Anti-NS1 ELISA result and non-valid titer results (ie, ‘Missing’ or coded ‘NR’ in the serology database).

Similarly, the following baseline statuses with 3 identical categories (ie, Immune, Non-immune and Missing) are defined for:

- Baseline dengue status: considering Anti-NS1 IgG
- Baseline YF status: considering neutralizing Abs against YF
- Baseline Zika status: considering neutralizing Abs against Zika

The LLOQ for YF and Zika and dengue neutralizing Abs is 10 (1/dil). Positive Anti-NS1 is defined as ≥ 9 ELISA unit/mL.

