4.4.4.3 Duration of the Study

The duration of the study is computed in days as follows: Latest date of all subjects (termination date, last visit date, date of last contact) – earliest date of all subjects (date of visit V01) +1.

5 Statistical Methods and Determination of Sample Size

The statistical analyses will be performed under the responsibility of the Sponsor’s Biostatistics platform using SAS® Version 9.4 software or later. The final analysis will be conducted once the 6-month safety data have been collected and the final database lock has occurred. No statistical adjustment is necessary because no hypotheses will be tested.

For descriptive purposes, the following statistics will be presented:

Table 5.1: Descriptive statistics produced

Baseline characteristics and follow-up description	Categorical data	Number of subjects. Percentage of subjects.
	Continuous data	Mean, standard deviation, quartiles, minimum, and maximum.
Clinical safety results	Categorical data (AEs)	Solicited: Number and percentage (95% CIs) of subjects. Unsolicited: Number and percentage (95% CIs) of subjects, and number of events.
	Categorical data (decrease in CD4 count, increase in HIV viral load, virologically-confirmed dengue case)	Number of subjects Percentage of subjects
Viremia	Categorical data	Number and percentage of subjects with a detectable or quantified viremia (possibly 95% CI of the percentage of the subjects)
	Continuous data	Mean, standard deviation, minimum and maximum (possibly median and quartiles) on quantified viremia data.
Immunogenicity results	Categorical data (cutoff)	Number and percentage (95% CIs) of subjects.
	Continuous data (titer/data)	Log10: Mean and standard deviation. Anti-Log10 (work on Log10 distribution, and anti-Log10 applied): Geometric mean, 95% CI of the geometric mean, quartiles, minimum, and maximum. Graphical representation by Reverse Cumulative Distribution Curve (RCDC).

The confidence interval (CI) for the single proportion will be calculated using the exact binomial method (Clopper-Pearson method, quoted by Newcombe (21), ie, using the inverse of the beta integral with SAS).

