5.2.1 Full Analysis Set

The FAS is defined as the subjects who received either CYD dengue vaccine or placebo and had blood sample drawn and valid post-injection serology results (ie, a result different from “not-reportable” [“NR”] or missing, for at least one dengue serotype).

Subjects will be analyzed by the vaccine treatment group to which they were randomized.

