5.2.2 Per-Protocol Analysis Set

The PPAS is a subset of the FAS. The subjects presenting with at least one of the following relevant protocol deviations will be excluded from the PPAS:

- Subject did not meet all protocol-specified inclusion criteria or met at least one of the protocol-specified exclusion criteria
- Subject did not complete the vaccination schedule
- Subject received a vaccine other than the one that he / she was randomized to receive
- Preparation and / or administration of vaccine was not done as per-protocol
- Subject did not receive vaccine in the proper time window
- Subject did not provide post-dose serology sample in the proper time window or a post-dose serology sample was not drawn
- Subject received a protocol-prohibited medication (see protocol Section 6.7)
- Subject’s post-injection serology sample did not produce a valid test result (ie, a result different from “NR” or missing, for at least one dengue serotype)
- Subject had other protocol violations that affected the subject’s immune response, as determined by the clinical team before locking the database.

Subjects will remain in the corresponding population as long as they do not meet one of the above criteria.

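### SAP 4.4.2.2 counts subjects of undetermined status as non-responders in the at-least-X-serotypes percentages, without saying so or planning to count them

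*SAP*

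**What the plan says.** SAP 4.4.2.2 derives a Yes/No/Missing variable per subject and visit.

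- **Yes:** at least X of the four serotype titers meet the threshold.
- **No:** "otherwise if at least one titer is available and does not meet the threshold the variable is derived to" No.
- **Missing:** "in the case no titer is available the variable will be missing".
- **Denominator:** "all the subjects with at least one titer available regardless of the serotype will be considered in the denominator".

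SAP 5.1.2.2 plans these outputs for the threshold of 10 (1/dil), "against at least 1, 2, 3, or 4 dengue serotypes with the parental dengue virus strains at each available time point", and again for various unspecified titer thresholds. SAP Table 5.1 gives the format for categorical immunogenicity results: "Number and percentage (95% CIs) of subjects". SAP 5.1.4 repeats the threshold-10 version by baseline flavivirus status.

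The analysis sets do not screen out partly missing serology. The FAS (SAP 5.2.1) needs a result that is not NR "or missing, for at least one dengue serotype". The PPAS (SAP 5.2.2) drops a subject whose "post-injection serology sample did not produce a valid test result", with validity defined in the same one-serotype way. SAP 5.3.2 and protocol 12.3.2 both say that missing immunogenicity values are not imputed.

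**The concern.** An at-least-X status needs four results, or enough of them to settle the question. The rule needs only one. Where results are partly missing and the status is open, the subject adds nothing to the numerator and one to the denominator, just as a measured non-responder does. That acts like imputing non-response, which sits awkwardly with the stated policy of no imputation.

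One type of profile also has no category on a literal reading. If every available titer passes but fewer than X are available (three passes and one NR at X=4), the subject is not Yes. The subject is not No either, because no available titer fails, and is not Missing, because titers exist. The denominator sentence still includes the subject.

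The next section, SAP 4.4.2.3, does provide an Undetermined class for composite flavivirus status, for when "subjects do not meet the criteria for at least one of the above three categories". Section 4.4.2.2 has no equivalent and plans no count of the subjects concerned. The trial tests no hypotheses, so its percentages and intervals are its results. In the baseline-status subgroups one subject weighs more.

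**Working it through.** **Plan's own figure.** Section 4.4.2.2 states none. The plan's only sample-size figure, a 95% chance of seeing an event of 3% incidence in 100 vaccinees, reproduces (1 − 0.97^100 = 95.2%) but has no bearing here.

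**Which profiles are affected.** Let s be the number of titers that pass, f the number that fail and m the number missing or NR, with s + f + m = 4. With at least one titer available, status is open when s < X ≤ s + m. Each serotype can pass, fail or be NR, which gives 3^4 = 81 profiles:

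| X | Undetermined profiles | Coded No | No category (f = 0) |
|---|---|---|---|
| 1 | 14 | 14 | 0 |
| 2 | 38 | 34 | 4 |
| 3 | 38 | 28 | 10 |
| 4 | 14 | 0 | 14 |

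At X=4 any failing titer makes No certain, so every open profile there is an uncategorised one. Partly NR subjects with s ≥ X are correctly Yes, and those with s + m < X are correctly No.

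**Direction and limit.** Take N subjects in the denominator, Y coded Yes and u undetermined, of whom r are truly Yes (0 ≤ r ≤ u). Reported = Y/N and true = (Y + r)/N. The shortfall is r/N, which is never negative and never more than u/N. With u = 0 it is zero.

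**Worked example (counts assumed).** Of 100 vaccine subjects, 76 pass all four, 20 have four titers and fail at least one, and 4 have three passes and one NR. X = 4.

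- SAP rule: 76/100 = 76.0% (Clopper-Pearson 95% CI 66.4–84.0).
- Upper bound: (76 + 4)/100 = 80.0%.
- Subjects with four valid titers: 76/96 = 79.2% (69.7–86.8).

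**Expected size at X=4 (NR rate q per serotype assumed).** If NR is independent across serotypes and unrelated to titer, a true responder is coded Yes only when all four results are valid:

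reported = true × (1 − q)^4 / (1 − q^4)

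| q | Factor | True 80% reported as |
|---|---|---|
| 0.5% | 0.980 | 78.4% |
| 1% | 0.961 | 76.8% |
| 2% | 0.922 | 73.8% |

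This formula does not need the titers themselves to be independent. If NR results cluster within samples at the same per-serotype rate, fewer subjects are partly missing and the loss is smaller.

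**Other X.** The table shows reported minus true in percentage points at q = 2%, with independent serotypes and a common per-serotype positivity p:

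| p | X=1 | X=2 | X=3 | X=4 |
|---|---|---|---|---|
| 0.9457 (true 80% at X=4) | 0.0 | −0.09 | −1.27 | −6.21 |
| 0.70 | −0.16 | −1.10 | −2.48 | −1.86 |
| 0.40 | −0.71 | −1.39 | −0.91 | −0.20 |

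In the first row the upper bound at X=4 is 80.37%. The undetermined share is therefore 80.37 − 73.79 = 6.58 points, and the loss of 6.21 lies within it, as it must.

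**Dropping undetermined subjects.** At q = 2% this gives 79.0% at X=4 against a true 80%. At X=1 with p = 0.20 it gives 60.6% against a true 59.0%, where the SAP rule gives 58.2%. Dropping can therefore err in either direction.

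**The case against.** The rule is prespecified, its denominator is stated in full, and counting only demonstrated responders is a defensible conservative convention. That stands. What is missing is a statement that this is the convention and a count of those it affects.

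The uncategorised profile is a wording gap. Whether it is coded No or left blank, the subject is in the denominator and not the numerator, so the percentage is the same.

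The size is hypothetical. No NR rate is given, protocol Table 5.1 plans serum for retesting, and the independence assumption pushes up the number of partly missing subjects. In the worked example the gap of 4 points between the bounds compares with a CI half-width of (84.0 − 66.4)/2 = 8.8 points. The low-positivity cases suit only the unspecified higher thresholds, since enrolment requires prior dengue exposure.

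The Undetermined class in SAP 4.4.2.3 is a weak precedent: it spans three assays, and the single-virus statuses there have only three categories. A reader could also gauge how many results are missing if the per-serotype tables use valid results as denominators, though not which subjects are undetermined.

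A reader might infer that every subject with an NR serotype is misclassified, or that the rule can never overstate response. The documents support neither. The first fails because many such subjects have a settled status. The second holds only for subjects in the denominator. If 80 of 100 are true responders and 4 of the 20 non-responders have all four serotypes NR (assumed), the rule reports 80/96 = 83.3%.

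**Conclusion.** The concern holds, and it is minor. SAP 4.4.2.2 counts undetermined subjects as non-responders, and the FAS and PPAS definitions let such subjects reach the tables. The resulting percentage is too low whenever an undetermined subject is truly a responder. The shortfall is capped by the undetermined share and is zero without such subjects. The X=4 losses of 1.6, 3.2 and 6.2 points from a true 80% rest on assumed NR rates of 0.5%, 1% and 2%, independent across serotypes and unrelated to titer.

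It would be tempting to conclude that samples with all serotypes NR do no harm, or that the vaccine/placebo comparison is distorted or preserved in some known direction. The documents support no such conclusion, because both depend on whether NR is related to titer, and the second also on NR rates by group. The affected tables are secondary and descriptive. GMTs, GMTRs and per-serotype percentages do not use this rule.

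**What to change.** In SAP 4.4.2.2:

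1. Keep the present convention, state that it is a lower bound, and explicitly code No where all available titers pass but fewer than X are available.
2. Report the number of undetermined subjects per group, visit, threshold and X.
3. Add an upper bound over the same denominator, counting undetermined subjects as Yes.

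A percentage among subjects with all four titers valid may be added as an optional sensitivity analysis, not as a replacement. It assumes that NR is unrelated to titer, and it discards some subjects whose status is settled; under the assumptions above the denominator shrinks by about 2.0%, 3.9% or 7.8% at 0.5%, 1% or 2% NR. Undetermined subjects should not simply be dropped, since that is itself biased.

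The cost is a few lines of derivation code, one count column, and one or two extra rows per table. Protocol 12.1.2.2 does not list these tables, so the protocol text need not change.
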